#### **Safety analysis**

All safety analyses will be based on the safety population. A secondary analysis will include only those patients receiving retreatment at 3 months. Results will be tabulated.

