4 TRIAL DESIGN

4.1 Overall study design and plan

This is a single center, single-arm, open-label, 60-month follow-up phase IIb clinical trial. Men with localized prostate cancer will receive TOOKAD® Soluble -VTP treatment under general anesthesia. Prior to the TOOKAD® Soluble- VTP treatment, patients will undergo routine ultrasound examination in the operating room for morphometric description of the prostate and to facilitate accurate treatment guidance for the treatment with TOOKAD® Soluble- VTP. Treatment will then be applied to the prostate gland as a focal therapy, hemiablation procedure designed to destroy the lobe of the prostate gland that contains the Gleason score 7 (3+4) cancer. Afterwards, patients will be followed for 12 months with clinical evaluation, questionnaires on QOL, erectile and urinary functions, and PSA testing. In addition, treatment outcomes will be assessed based on prostate biopsy results at 3, 12, 24, 36, 48 and 60 months after the TOOKAD® Soluble treatment. All patients will undergo biopsy at 3 and 12 months after the TOOKAD® treatment. Thereafter, biopsy will be performed for cause per institutional standards. If the Month 3 biopsy is positive for any cancer patients will be allowed a single re-treatment by TOOKAD® Soluble VTP. However, patients with evidence of clinical deterioration on the same side such as worsening Gleason score, increased core involvement with cancer tumor grades on the 3-month biopsy and/or rising PSA will be withdrawn from the study and proceed with standard care. In addition, patients who experience treatment-related Grade 3-4 adverse events during their first treatment will not be re-treated at month 3, will be withdrawn and proceed with standard care if the month-3 biopsy contains cancer on the same or contralateral side, unless justification for continuing on study is specifically sought and approved from the IRB.

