9.3 Documentation of Adverse Events

AE collection will begin after consent has been obtained and continue until the final visit. Every AE or symptom will be recorded in the CRF and will include:

1. nature (brief description)
2. date and time of onset
3. date and time of resolution
4. seriousness (see Section 9.1 for definition)
5. relationship (unrelated, unlikely, possible, probable, or very likely) to the study drug estimated by the investigator
6. if study-related:
 - study drug-related
 - study device-related
 - study technical procedure-related
7. action taken
8. outcome

On the basis of the occurrence and intensity of AEs, coupled with results of any other observations, the Investigator, at his discretion and following discussion with the Sponsor, may decide to withdraw a subject or prematurely end the study for reasons of clinical safety. The date of such termination will be recorded and appropriate treatment instituted at the discretion of the investigator or sub-investigator.

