10.5.1 Analysis of adverse events

Distinctions will be made between the adverse events not related to the study treatment, the technical procedure or the study device, and those related to any of the above.

Numbers and frequencies of AEs will be tabulated and the proportions of patients exhibiting each AE will be displayed. The adverse events will be classified according to the MedDRA nomenclature. The treatment-emergent adverse events (which happen or worsen after the first study drug intake) will be summarised by System Organ Class (SOC) and preferred term. In addition, the adverse events will be classified according to the National Cancer Institute (NCI) Common Terminology Criteria for Adverse Events (CTCAE) which is a safety endpoint of the study. Tabulations will also be made for the System Organ Class (SOC, current MedDRA version), intensity, relationship, seriousness, and attribution corresponding to each AE. Separate tabulations will be made for SAEs.

The treatment-emergent adverse events (which occurred or worsened after the first study drug intake) will be summarised by primary SOC system and preferred term.

For pre-treatment events listings will be provided. For medical/surgical history and additional examinations listings will be provided.

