#### **Adverse events**

Distinctions will be made between the adverse events not related to the study treatment, related to the study treatment or related to the technical procedure of the VTP. Frequencies of AEs will be tabulated by treatment arm and the proportions of patients exhibiting each AE will be displayed. The adverse events will be classified according to MedDRA version 23.1 or higher.

The treatment-emergent adverse events (adverse events starting after the treatment) will be summarized by System Organ Class (SOC) and preferred term. In addition, the adverse events will be classified according to the NCI Common Terminology Criteria for Adverse Events which is a safety end point of the study. Tabulations will also be made for the System Organ Class, intensity, relationship, seriousness, and attribution corresponding to each AE. Separate tabulations will be made for SAEs.

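### The SAP sets no start point at the second VTP, so adverse events from the first and second sessions are tabulated together in the re-treated men

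*SAP*

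**What the plan says.** The SAP's Safety analysis section gives re-treatment one sentence, "A secondary analysis will include only those patients receiving retreatment at 3 months", and adds that results will be tabulated. It names the men but gives no date from which their events count.

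The SAP's Adverse events section continues: "The treatment-emergent adverse events (adverse events starting after the treatment) will be summarized", by system organ class and preferred term, with the proportion of patients showing each event. Treatment is in the singular. Protocol section 10.5.1 defines treatment-emergent events as those "which happen or worsen after the first study drug intake". On attribution the SAP says "Distinctions will be made between the adverse events not related to the study treatment, related to the study treatment or related to the technical procedure"; nothing assigns an event to the first or second session. Tabulation is by treatment arm, and this trial has one.

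On the second session itself:
- The Protocol synopsis (Treatment conditions) allows re-treatment 2-4 months after the Month 3 biopsy, with the same drug and light parameters, to one or both lobes.
- Section 6.4.10 leaves the visit schedule unchanged after re-treatment.
- Section 4.1 says that "patients who experience treatment-related Grade 3-4 adverse events during their first treatment will not be re-treated at month 3", with the qualifier "unless justification for continuing on study is specifically sought and approved from the IRB".
- Section 9.3 records the "date and time of onset" of every event.

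**The concern.** Describing adverse events is secondary objective 7 of the trial, and some men will receive a second VTP. A reader of the report will want to know what happened after that second session. A table restricted by person and not by time cannot tell them directly, because each proportion covers everything from the first VTP to Month 60. The all-patient table has a related weakness: it mixes men followed after one session with men followed after two, so no planned table gives a clean first-course rate either.

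What is at stake is the readability of the safety description. The primary endpoint and the conduct of the trial are not affected.

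**Working it through.** The documents give no expected number of re-treated men and no second-session event rate, so there is no plan figure to reproduce. The check has five steps.

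**1. What the definitions produce.** Take a man with one event at Month 1 and another a week after his second VTP. Both start after the treatment (SAP) and both occur after the first drug intake (Protocol 10.5.1). He is in the safety population and in the re-treated subset. Both events enter the same table, and if they share a preferred term they count once. The SAP does not state that events are pooled. Pooling is what results from programming these definitions with no second start point.

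**2. Whether the visit label can stand in for the split.** The Month 3 biopsy falls at 2.5 to 3.5 months (±2 weeks). Adding 2 to 4 months puts the second VTP at about Month 4.5 to 7.5. The Month 6 visit has a window of ±2 months, so Month 4 to 8. It can come before the second VTP in one man and after it in another. Only the actual date separates the sessions.

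**3. Size for all-grade related events (illustration).** Let q1 and q2 be the proportions of men with at least one related event after the first and second VTP. Assuming independent sessions, the pooled proportion is 1 − (1 − q1)(1 − q2). Protocol section 2.2.4 gives 78.7% with an AE related to drug, device or procedure in the European phase III trial; use it for q1. The q2 values are assumptions.

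| True second-session rate q2 | Pooled row: 1 − 0.213 × (1 − q2) |
|---|---|
| 0% | 78.7% |
| 20% | 83.0% |
| 40% | 87.2% |
| 78.7% | 95.5% |
| 90% | 97.9% |

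Going from 20% to 90% moves the pooled row by 0.213 × 70 = 14.9 points. For a row with q1 = 50%, the same change moves it from 60% to 95%, or 35 points. The shrinkage factor is 1 − q1, so compression is strong only where first-session events are common. For a rare event there is little compression, but the row still does not show which session the event followed.

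**4. Treatment-related grade 3-4 events.** Under the section 4.1 bar, q1 in re-treated men is about 0. Taking the 9% grade 3 rate reported for the Latin American trial (section 2.2.4) as an illustrative q2, the pooled row is 1 − (1 − 0)(1 − 0.09) = 9%, equal to the second-session rate. In unselected men it would be 1 − 0.91² = 17.2%. The bar therefore leaves almost nothing from the first session to pool.

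**5. Precision after a split.** The number re-treated is an assumption: 10% to 30% of the 50 planned men gives 5 to 15. With no event of a given type after the second VTP, the one-sided 95% exact upper bound is 1 − 0.05^(1/n): 45%, 26% and 18% for n = 5, 10 and 15. The upper limit of the two-sided 95% interval that Protocol 10.2.2.3 prescribes is 1 − 0.025^(1/n): 52%, 31% and 22%.

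**The case against.** The strongest case against the point is that nothing is lost. Protocol 10.2.1 and the SAP (Statistical plan and methods) promise listings by subject, onset is recorded, and with so few re-treated men a reader could sort the events by hand. IPSS, IIEF and laboratory shifts are summarised by visit: Months 1 and 3 precede the second VTP and Month 12 follows it. The 78.7% figure is for any related event, whereas the SAP tabulates by preferred term, for which the documents give no rates. The stated objective is only to describe adverse events, not to compare courses.

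Most of this stands, and it limits the point. The information is recoverable, so it would be wrong to say that the trial cannot describe the second session. The illustration applies to an any-related-event row and rests on independence. What remains is that no summary table shows second-session events, the by-visit outputs leave Month 6 ambiguous, and a listing does not replace a tabulated proportion with its denominator.

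A reader might also infer that selecting men who tolerated the first VTP makes re-treatment look safe for severe events. The documents do not support this. The bar removes first-session related grade 3-4 events, so those that appear come almost entirely from the second VTP and are shown over the number of re-treated men, undiluted. Nor is the selection a bias to correct: apart from exceptions approved by the IRB, these are the only men the rule re-treats. It needs a footnote.

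**Conclusion.** The point holds in a limited form. The plan defines no window after the second VTP, and its treatment-emergent definitions put both sessions into one count. This blurs all-grade, lower-grade, unrelated and overall AE and SAE figures for the second session. For an any-related-event row the loss could be large (70 points reduced to about 15, given q1 = 78.7% and independence); for individual terms its size is unknown.

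Treatment-related grade 3-4 events are not materially masked. That conclusion depends on how the bar is applied, and its wording varies. Section 4.1 limits it to treatment-related events and allows an IRB exception; section 6.2.3 mentions neither condition. These passages need to be reconciled, because they decide what the footnote to the table can say.

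The matter is worth settling before the safety tables are programmed. It does not put the safety conclusions of the trial as a whole in doubt.

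**What to change.** This changes the analysis text only.

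1. SAP, Safety analysis: for re-treated men, tabulate AEs and SAEs in two columns, onset before and onset on or after the actual date of the second VTP, each with n and an exact confidence interval. Replace the reference to re-treatment at 3 months with that date, since the second VTP falls later.
2. All-patient table: show first-course events, with follow-up cut at the second VTP, as a separate column.
3. Align the treatment-emergent definitions in Protocol 10.5.1 and the SAP. The Protocol includes worsening and the SAP does not. State which column takes an event that began before the second VTP and worsened after it.
4. Footnote three things: the subset normally excludes men with grade 3-4 events at the first treatment; re-treatment may cover both lobes, so exposure can differ between columns; and no Day 7 or Month 1 visit is tied to the second VTP (section 6.4.10). Because of the last, ascertainment differs between the two periods even if windows of equal length are used.

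The cost is SAP wording and one extra table split from onset dates already collected. The downside is imprecision: the documents do not say how many men will be re-treated, and with 5 to 15 the intervals will be wide. The split describes the second session and will not support a formal comparison with the first.

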#### **Adverse events**

Distinctions will be made between the adverse events not related to the study treatment, related to the study treatment or related to the technical procedure of the VTP. Frequencies of AEs will be tabulated by treatment arm and the proportions of patients exhibiting each AE will be displayed. The adverse events will be classified according to MedDRA version 23.1 or higher.

The treatment-emergent adverse events (adverse events starting after the treatment) will be summarized by System Organ Class (SOC) and preferred term. In addition, the adverse events will be classified according to the NCI Common Terminology Criteria for Adverse Events which is a safety end point of the study. Tabulations will also be made for the System Organ Class, intensity, relationship, seriousness, and attribution corresponding to each AE. Separate tabulations will be made for SAEs.

**IPSS (International Prostate Symptom Score) questionnaire**

The IPSS score will be calculated as the sum of answers to questions 1 to 7. Prostate related quality of life will be derived from question 8. Descriptive summaries of change from baseline scores at each assessment visit will be provided for both Observed Cases and a multiple imputation method approaches.

**IIEF (International Index of Erectile Function) questionnaire**

All items will be scored in 5 domains as follows:

- Erectile Function: sum of items 1, 2, 3, 4, 5 and 15 (score range: 1-30).
- Orgasmic Function: sum of items 9 and 10 (score range: 0-10).
- Sexual Desire: sum of items 11 and 12 (score range: 2-10).
- Intercourse Satisfaction: sum of items 6, 7 and 8 (score range: 0-15).
- Overall Satisfaction: sum of items 13 and 14 (score range: 2-10).

Descriptive summaries of the change from baseline will be provided for both Observed Cases and a multiple imputation method approaches.

In addition the erectile function score will be dichotomized as 22 or above vs. 21 and below and the proportion of cases with new onset erectile dysfunction at each timepoint (i.e. baseline score  $\geq 22$  but follow-up score  $< 22$ ) will be reported. For a secondary analysis, new onset erectile dysfunction will be described as baseline score  $\geq 22$ , follow-up score  $< 22$  and change from baseline of more than 2 points.

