7.2 Patients' questionnaires on erectile dysfunction and urinary symptoms

The following questionnaires will be applied to all patients to assess erectile function and urinary symptoms at entry and at months 1, 3, 6, 12, 24, 36, 48 and 60:

- IIEF-15 for erectile function

The International Index of Erectile Function (IIEF) relates to the following areas: confidence in erection; erection sufficient for penetration; maintaining of erection; difficulty to maintain erection for completion; satisfactory intercourse. Subjects will be asked to give their response to each of the areas using a 6-point scale (0=no sexuality, 5=best response).

- IPSS for lower urinary tract symptoms

The International Prostate Symptom Score (IPSS) is an 8-question questionnaire focused on urinary symptoms with one general question about urinary symptoms. The questions relate to the following areas: sensation of bladder emptying; frequency of urination; stops when urinating; difficulties to postpone urination; urinary steam; beginning of urination; night urination. Subjects will be asked to give their response to each of the areas using a 6-point scale (0=none or normal, 5=worse response).

These questionnaires will encompass the consequences of all treatments, including additional radical therapy potentially used by patients. Scores for each one of the scales will be calculated regardless of failure or not, and additional treatment or not.

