### **Secondary endpoints**

- Binary response to treatment defined as the absence of any Gleason grade 4 or 5 biopsy on or before months 24, 36, 48 and 60. If a subject is retreated following a positive biopsy at 3 months and subsequent biopsy shows absence of Gleason grade 4 or 5, the subject will be considered to have responded
- Binary response to treatment defined as the absence of any Gleason grade 4 or 5 biopsy on or before months 12, 24, 36, 48 and 60 in the treated lobe. If a subject is retreated following a positive biopsy at 3 months and subsequent biopsy shows absence of Gleason grade 4 or 5, the subject will be considered to have responded
- Binary response to treatment defined as the absence of any prostate cancer on biopsy on or before months 3, 12, 24, 36, 48 and 60. If a subject is retreated following a positive biopsy at 3 months and subsequent biopsy shows absence of any cancer, the subject will be considered to have responded
- Binary response to treatment defined as the absence of any prostate cancer on biopsy on or before months 3, 12, 24, 36, 48 and 60 in the treated lobe. If a subject is retreated following a positive biopsy at 3 months and subsequent biopsy shows absence of any cancer, the subject will be considered to have responded
- Changes in biopsy result between 3, 12, 24, 36, 48 and 60 months after the procedure
- Patients' reported outcome measures (PROMs) impairment: urinary symptoms using IPSS and erectile functions using IIEF prior to treatment beginning and then 1, 3, 6, 12, 24, 36, 48 and 60 months after completing treatment.

Quality of life is assessed using validated questionnaires. The IPSS comprises seven questions on the urinary symptoms plus one general question about the QOL related to urinary symptoms, whereas the IIEF comprises 15 questions. For both questionnaires, patients self-rate their responses: for the IPSS, using a six-point scale where 0 indicates 'none' or 'normal', whereas 5 indicates the worst response; for the

IIEF, using a five- or six-point scale where 0 indicates 'no sexual activity', and 5 indicates the best response (questions 1 to 10), or where 1 indicates the worst response and 5 the best response (questions 11 to 15).

- Rate of adverse events following treatment

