***Handling of missing data and/or invalid data and outliers*****IIEF questionnaire**

Subscale scores with at least 1 but not more than 50% missing items will be imputed using the formula:  $S = s \times T \div t$  where s is the observed score, S is the imputed score, T is the maximum total score for the subscale and t is the maximum score possible from the completed questions. Missing subscale scores will be imputed using a multiple imputation method (Markov Chain Monte Carlo method).

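### The SAP's new-onset erectile dysfunction rule counts a man who reports no sexual activity as a new case and does not show how many such men there are

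*SAP*

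**What the plan says.** The SAP's IIEF section defines the domain as "Erectile Function: sum of items 1, 2, 3, 4, 5 and 15 (score range: 1-30"). It then says that "the erectile function score will be dichotomized as 22 or above vs. 21 and below" and that it will report "the proportion of cases with new onset erectile dysfunction at each timepoint", where a new case has a baseline of at least 22 and a follow-up below 22. A secondary analysis adds a third condition: "and change from baseline of more than 2 points".

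The item coding stands under Secondary endpoints in the SAP. For the first ten IIEF items the coding reads "where 0 indicates 'no sexual activity', and 5 indicates the best response (questions 1 to 10"). The remaining items, among them item 15 of this domain, have no zero: "or where 1 indicates the worst response and 5 the best response (questions 11 to 15"). Protocol section 10.4.1 gives the same coding, and Protocol section 7.2 describes a "6-point scale (0=no sexuality, 5=best response").

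The only special handling of IIEF items is the SAP's missing-data rule: "Subscale scores with at least 1 but not more than 50% missing items will be imputed using the formula". Neither document recodes, excludes or separately reports men whose zeros mean inactivity. Protocol section 10.4.2 refers secondary variables to general descriptive methods.

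**The concern.** By the documents' own coding, a zero on items 1 to 5 records that the man was not sexually active. It does not record that he tried and failed. The rule adds these zeros into the domain and reads a low total as dysfunction. A man who had a good score at baseline and is inactive at a later visit for any reason, such as illness or loss of a partner, enters the table as a new case.

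The proportion will be read as a statement about the treatment. Describing changes in erectile function is secondary objective 6. Protocol section 2.2.4 presents preserved erectile function as a strength of the procedure, and section 2.1 quotes erectile dysfunction in 30-70% of men after whole-gland therapy. There is no control arm to show how much inactivity would occur anyway, so the reader cannot separate inactivity from loss of function.

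**Working it through.** **Inputs.** Domain items 1 to 5 and 15, cut-off 22, and the more-than-2-point condition: SAP, IIEF questionnaire. Items 1 to 5 scored 0 to 5 and item 15 scored 1 to 5: SAP, Secondary endpoints.

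**1. Reproduce the stated range.** Minimum = 5 × 0 + 1 = 1. Maximum = 5 × 5 + 5 = 30. This matches the SAP's 1-30. The minimum of 1 is reached only if the zeros enter the sum, so they are meant to count.

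**2. Man inactive at follow-up.** Items 1 to 5 all 0: domain = 5 × 0 + item 15 = 1 to 5, always below 22.

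**3. More-than-2-point condition.** From a baseline of 22 to 30, the smallest fall is 22 − 5 = 17 and the largest is 30 − 1 = 29. The condition is always met, so he is a new case under both definitions.

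**4. Part-zero answers.** With k zeros among items 1 to 5, the highest possible domain score is 5 × (5 − k) + 5:

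| Zeros on items 1 to 5 | Highest domain score |
|---|---|
| 0 | 30 |
| 1 | 25 |
| 2 | 20 |
| 3 | 15 |
| 4 | 10 |
| 5 | 5 |

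Two zeros are enough to fall below 22. Under the secondary definition there is one exception: with exactly two zeros, a baseline of 22 and a follow-up of 20, the fall is 2, which is not more than 2. With three zeros the smallest fall is 22 − 15 = 7, so the condition is always met.

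**5. Does the missing-data rule change this?** A zero is an answer, so it is not imputed. If other items are missing, the score is prorated. With n of six items answered and two of them zero, the highest prorated score is 5(n − 2) × 30 / (5n) = 30(n − 2)/n. That is 20, 18, 15 and 10 for n = 6, 5, 4 and 3, all below 22.

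**6. Who is exposed.** Only men with a baseline of 22 or more. A man inactive at baseline scores 5 or less and cannot be a new case.

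**7. Size, by assumption only.** The documents give neither the number of men with a baseline of 22 or more nor any inactivity rate. If that number is 30, one inactive man adds at most 1/30 = 3.3 percentage points. If all 50 planned patients were the denominator, he adds at most 1/50 = 2.0 points. He adds nothing if he would have scored below 22 had he been active.

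**The case against.** The strongest reply is that this is how the questionnaire is scored. The documents call it validated, the 1-30 range requires the zeros to count, and the cut-off is applied consistently to that score. Inactivity can also be a consequence of dysfunction, so removing these men would flatter the treatment. The effect overstates dysfunction, which is conservative for the functional claim. No test or decision depends on the proportion. Inactivity is also partly visible elsewhere: the Intercourse Satisfaction domain (items 6 to 8) falls to 0 with inactivity, Sexual Desire (items 11 and 12) has no inactivity code, and the SAP lists the collected data by subject.

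Most of this stands. The domain score is not an error, the planned proportion should stay, and the direction is against the treatment. What does not fall away is the label. The SAP gives a response one meaning and then reports it, undifferentiated, under another. Domain summaries and listings do not give the reader the number of new cases that rest on inactivity.

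Three stronger readings are tempting, and the documents do not support them:

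- A reader might infer an inflation of 10 to 20 points, from 3 to 6 inactive men among 30 (3/30 and 6/30). All these inputs are assumed, and the result is a ceiling, because it supposes that every one of these men would otherwise have scored 22 or more.
- A reader might infer that the more-than-2-point version gives false reassurance. The SAP calls it a secondary analysis and nowhere says that it addresses inactivity. On its face it removes small falls across the cut-off.
- A reader might infer that Months 1 and 3 are the most exposed. No text requires or reports abstinence. The Month 1 questionnaire precedes any post-treatment biopsy, and the Month 3 questionnaire belongs to the same visit as the first one.

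**Conclusion.** The point holds as a limited one about reporting. On the stated coding, a man with a baseline of 22 or more who answers 0 on all of items 1 to 5 is counted as new-onset erectile dysfunction under both definitions, with a fall of at least 17 points. Two zeros are enough under the main definition, and under the secondary one apart from the single case of a fall from 22 to 20. These results follow from the SAP's own scoring and need no assumption.

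The direction is to overstate dysfunction. The size is unknown. The 3.3 points per man is an illustration that rests on an assumed 30 men and is a maximum. The outcome is descriptive and the primary endpoint is not affected. This is a worthwhile improvement and not a flaw that threatens the trial's conclusions.

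**What to change.** Keep the planned new-onset proportion. For both definitions, add at each visit, among men with a baseline of 22 or more:

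- the number who answered 0 on all of items 1 to 5;
- the number with two to four zeros on items 1 to 5;
- as a sensitivity figure, the new-onset proportion among men with fewer than two zeros on those items, with its denominator.

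Flagging only the all-zero men would not be enough, since men with two to four zeros would remain in the active group and still fall below 22.

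The cost is a few lines of SAP text and additional table columns, from item responses already collected. The downside is that inactivity can itself result from dysfunction, so the sensitivity figure may be too low. It should stand beside the planned figure as a sensitivity analysis. The two should not be presented as strict bounds on the true rate.
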